4.4.3. Other Secondary Efficacy Endpoints

Descriptive statistics will be used to summarize the following additional secondary efficacy endpoints. Descriptive statistics for continuous data will include means, medians, standard deviations and ranges, and categorical data will provide frequencies and percentages.

4.4.3.1. Absolute neutrophil count trough values by cycle

Absolute neutrophil count (ANC) will be summarized by descriptive statistics for cycle trough values (which are lower than the ANC value at baseline for that cycle) and changes from baseline between the start and end of each cycle. Cycle trough values for ANC will be summarized descriptively for Part II of the study to evaluate confounding effects of G-CSF administration separately by the presence or absence of G-CSF administration during treatment.

4.4.3.2. Absolute neutrophil counts, platelet counts, absolute lymphocyte counts, and hemoglobin over time

Hematology parameters, including ANC, platelet count, absolute lymphocyte count (ALC), and hemoglobin (HGB) will be summarized by treatment group using descriptive statistics based on laboratory hematology results at baseline and each visit time point. Listing will be provided for detials. ANC will be summarized descriptively to evaluate confounding effects of G-CSF administration separately according to the presence or absence of G-CSF administration during treatment.

Time-line plots for mean ANC, platelet count, ALC, HGB, and change from baseline in HGB (with 95% confidence intervals) will be provided by cycle.

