2.2. Study endpoints

Part I (Safety Run-in and PK Evaluation Part):

Primary Endpoint:

- PK profile (C_{max}, AUC and other PK parameters);
- Safety and tolerability: adverse events, laboratory abnormalities, etc.;
- Duration of severe neutropenia in Cycle 1 (DSN);

Key Secondary Endpoints:

- Occurrence of severe neutropenia (SN);
- Occurrence of red blood cell transfusion (on/after Week 5);
- Granulocyte colony stimulating factor (G-CSF) use rate;
- Composite endpoint-major adverse hematologic event (Any of the following):
 - All-cause hospitalization;
 - All-cause chemotherapy dose reductions;
 - Febrile neutropenia;
 - SN prolongation (lasting > 5 days);
 - RBC transfusion on/after Week 5.

Other secondary endpoints:

• Occurrence of Grade 3 and 4 hematological toxicities;

- Absolute neutrophil count trough by cycle;
- Absolute neutrophil count, platelet count, absolute lymphocyte count, and hemoglobin over time;
- Erythropoiesis stimulating agent (ESA) use rate;
- Recombinant human interleukin -11 use rate;
- Thrombopoietin (TPO) use;
- Occurrence of intravenous or oral antibiotic administration;
- Occurrence of infectious serious adverse events;
- Occurrence of serious adverse events of lung infection;
- Occurrence of febrile neutropenia;
- Occurrence of platelet transfusion;
- Objective tumor response rate (ORR);
- Disease control rate (DCR).

Exploratory Endpoints

- Progression-free survival (PFS);
- Overall survival (OS);
- Population pharmacokinetic profile.

Part II (randomized, double-blind part):

Primary Endpoint:

• Duration of severe neutropenia in Cycle 1 (DSN);

Key Secondary Endpoints:

- Occurrence of severe neutropenia (SN);
- Occurrence of red blood cell transfusion (on/after Week 5);
- Granulocyte colony stimulating factor (G-CSF) use rate;
- Composite endpoint major adverse hematologic event (Any of the following):
 - All-cause hospitalization;
 - All-cause chemotherapy dose reductions;
 - Febrile neutropenia;
 - SN prolongation (lasting > 5 days);
 - RBC transfusion on/after Week 5.

Other secondary endpoints:

• Occurrence of Grade 3 and 4 hematological toxicities;

- Absolute neutrophil count trough by cycle;
- Absolute neutrophil count, platelet count, absolute lymphocyte count, and hemoglobin over time;
- Erythropoiesis stimulating agent (ESA) use rate;
- Rate of recombinant human interleukin -11 use;
- Thrombopoietin (TPO) use;
- Occurrence of intravenous or oral antibiotic administration;

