4.1. General Principles

Descriptive statistics (mean, standard deviation, median, range, etc.) will be used to summarize continuous variables, and counts and proportions will be used to summarize categorical variables by treatment group. For time-to-event variables, Kaplan-Meier method will be used to estimate the survival function and estimate the median survival time and its 95% confidence interval, and survival curves will be provided.

Unless otherwise specified, the cycle baseline measurement for Cycle 1 is defined as the last available valid measurement within 7 days before the start of study medication on Cycle 1 Day 1; the baseline measurement for subsequent cycles is defined as the last available valid measurement within 3 days before the start of study medication on Cycle 1 Day 1. Unless otherwise specified, study baseline measurements are defined as the last available valid measurement prior to the first dose of study drug. If the last valid measurement coincides with the start date of the first study drug administration, the measurement will be considered as baseline measurement. Adverse events or concomitant medications that occurred on the day of the first dose of study drug are considered postbaseline.

The start date of each cycle is defined as the first day of the cycle, i.e., the date of the first study drug administration of the cycle; the end date of each cycle is defined as the start date of the next cycle, or the first day of the cycle +36 days if the next cycle is not entered.

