4.4.1.1. Strategy 1: Missing ANC values not imputed

For patients who experienced at least 1 episode of severe neutropenia (SN) within each cycle, a DSN is defined as the number of days from the date of the first absolute neutrophil count (ANC) value $< 0.5 \times 10^{9}$ /L in that cycle to the date of the first ANC value $\ge 0.5 \times 10^{9}$ /L that met the following requirements: (1) occurred after an ANC value $< 0.5 \times 10^{9}$ /L, and (2) no other ANC value $< 0.5 \times 10^{9}$ /L occurred between that date and the end of that cycle (otherwise the SN event is considered not resolved at the end of that cycle). If a patient does not experience any SN during the cycle, DSN will be counted as 0 for that cycle. Exceptions will be handled using the following rules:

- If the SN event is not resolved at the end of the cycle, the DSN will be calculated as above, but the end date is the end date of the cycle;
- If a patient dies during the period of the SN event, the DSN will be calculated as described above, but the end date is the date of death;
- If a patient withdraws consent or is lost to follow-up during the period of the SN event, the DSN will be calculated as described above, but the end date will be the last ANC assessment date before the end of the study.

Nonparametric analysis of covariance (Nonparametric ANCOVA) will be used to evaluate DSN-based differences in efficacy between the test and placebo groups. The nonparametric covariance model will include covariates of baseline ANC study value as a continuous variable, and fixed effects of number of lines of treatment (1st line versus 2nd/3rd line), ECOG (0 or 1 versus 2), brain metastases (yes versus no), and treatment arm (Trilaciclib versus placebo) as categorical variables. Stratification will be combined or reduced appropriately if the number of patients within a stratum is small. The p-value for the 2-sided test will be calculated from the model, and it will be provided the difference in means between the two treatment groups and its 95% confidence interval (CI) based on Satterthwaite t-test, as well as the median difference between the groups and its 95% confidence interval estimated using Hodges-Lehmann.

In addition, DSN will be summarized for each cycle by treatment group using descriptive statistics.

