4.11. Handling of Missing Data

Every effort should be made to minimize the generation of missing data. Missing data will not be imputed unless otherwise specified. For time-to-event endpoints in efficacy, missing data will be handled based on statistical analysis model; for response rate in efficacy (such as ORR, DCR), missing data will be considered as non-responder and included in the analysis.

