g. Hematology includes: white blood cell (WBC), red blood cell (RBC), hemoglobin (Hb), platelet (PLT), hematocrit (HCT), neutrophil (NEU), eosinophil (EOS), basophil (BAS), monocyte (MON), lymphocyte (LYM), etc.; hematology in Cycle 1 is scheduled on Day 1 (within 24 hours before administration), Day 3, Day 8, Day 10, Day 15, and baseline hematology should be performed within 24 hours before the first study dose; hematology in other cycles is performed on Days 1 and 8 of each cycle, and the examination on Day 1 of each cycle is performed before administration. Subjects were eligible for chemotherapy administration as determined by predose hematology results on Day 1 of each cycle.

Product: Trilaciclib Protocol Number: B02B0)801-TRILA-3	01			Jiangsu S	imcere Pha	armaceutica	l Co., Ltd					
	Saraanin	Treatment Period ^a (21 days per cycle, 6 cycles)											Survival
	g Period		Cycle 1 Cycle 2 and above									Safety Visit ^b	Follow-up ^c
	D-21 ~ - 1	D1	D2	D3	D8	D10	D15	D1	D2	D3	D8	+ 30 days	Every 60 days
Window (Days) ± 1 ± 1 ± 1 ± 3 ± 1 ± 7													

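### SAP 4.4.3.1 counts an ANC trough only when it lies below the cycle baseline, so patient-cycles without a fall have no trough value and the summary conditions on a post-randomisation outcome

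*SAP*

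**What the plan says.** Protocol 2.2 lists the endpoint without any condition: "Absolute neutrophil count trough by cycle". SAP 4.4.3.1 adds one. It summarises cycle troughs, in parentheses "which are lower than the ANC value at baseline for that cycle", together with "changes from baseline between the start and end of each cycle", and repeats the trough summary by presence or absence of G-CSF during treatment.

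No value is assigned to a cycle without a fall, and SAP 4.11 states: "Missing data will not be imputed unless otherwise specified". The primary endpoint does have such a rule, in SAP 4.4.1.1: "If a patient does not experience any SN during the cycle, DSN will be counted as 0 for that cycle".

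Sampling differs by cycle. For EC, SAP Appendix 2 says "hematology in Cycle 1 is scheduled on Day 1 (within 24 hours before administration), Day 3, Day 8, Day 10, Day 15"; later, "hematology in other cycles is performed on Days 1 and 8 of each cycle". For topotecan, Cycle 1 has Days 1, 5, 10, 12 and 15, and later cycles have Days 1 and 10. Under SAP 4.1 a cycle ends at the start of the next cycle, or 36 days after its own Day 1 if no further cycle is started.

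**The concern.** A trough is ordinarily the lowest count in the cycle. Here it must also be below baseline. A patient-cycle that fails this has nothing to summarise, and nothing is imputed.

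The condition is settled after randomisation. Trilaciclib is meant to change it, and so does G-CSF, which Protocol 5.6 leaves to the investigator after Cycle 1. The summary therefore compares selected patient-cycles that may be selected differently in the two arms. The change from baseline to trough is also cut off at zero, so its mean, median and range cannot show a cycle in which the count held or rose. At stake is the interpretation of one descriptive endpoint.

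**Working it through.** **Text.** Let B be the cycle baseline and T the lowest post-dose ANC in the cycle. The SAP trough exists only if T < B, so every reported change T − B is below zero. If T ≥ B, no value is defined and none is imputed.

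**Where it can occur.** Cycle 1 has four scheduled post-dose counts in either regimen, plus the next Day 1, so T ≥ B should be uncommon. Later cycles have one mid-cycle count (Day 8 or Day 10) plus the next Day 1. The last cycle has no next Day 1; the safety-visit count may or may not fall within its 36 days.

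**Size.** The plan gives no figure to reproduce, so every input below is an assumption except the two G-CSF rates. Baseline is log-normal, median 4 × 10⁹/L, log SD 0.4. The Day 8 to baseline ratio has median 0.75 on trilaciclib and 0.50 on placebo, log SD 0.45 to 0.5. The next Day 1 ratio is as shown in the table. T is B times the smaller ratio.

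With Day 8 alone and log SD 0.5, the result follows by hand for ratio median m:
- Mean baseline = 4 × exp(0.4²/2) = 4.333.
- Mean ratio, all cycles = m × exp(0.125).
- Mean ratio, restricted = m × exp(0.125) × Φ((−ln m − 0.25)/0.5) / Φ(−ln m/0.5).
- Trilaciclib: 0.850 for all cycles; 0.850 × 0.530/0.718 = 0.628 restricted. Mean troughs 3.683 and 2.721; excluded 1 − 0.718 = 28%.
- Placebo: 0.567 for all cycles; 0.567 × 0.812/0.917 = 0.502 restricted. Mean troughs 2.455 and 2.174; excluded 1 − 0.917 = 8%.
- Difference: 3.683 − 2.455 = 1.228 becomes 2.721 − 2.174 = 0.547. Shrinkage 1 − 0.547/1.228 = about 55%.

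The other rows were simulated with two million patient-cycles per arm and Day 8 log SD 0.45. The G-CSF rows use a Day 8 ratio with median 1.3 in cycles with G-CSF. Their rates, 28.5% on trilaciclib and 56.3% on placebo, are the integrated-analysis figures in Protocol Table 3.

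| Next Day 1 ratio (median, log SD) | G-CSF cycles, trilaciclib / placebo | Excluded, trilaciclib / placebo | Mean difference, all → restricted (× 10⁹/L) | Change |
|---|---|---|---|---|
| 0.8, 0.2 | none | 3.5% / 0.8% | 0.65 → 0.60 | about 8% smaller |
| 1.0, 0.4 | none | 13.1% / 3.1% | 0.81 → 0.58 | about 28% smaller |
| none (Day 8 only) | none | 28% / 8% | 1.23 → 0.55 | about 55% smaller |
| 1.0, 0.4 | 14.25% / 28.15% (half rates) | 16.3% / 12.3% | 0.45 → 0.42 | about 7% smaller |
| 1.0, 0.4 | 28.5% / 56.3% | 19.5% / 21.6% | 0.09 → 0.21 | larger |

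The 8% and 55% are not bounds. A next Day 1 ratio with median 0.7 and log SD 0.2, without G-CSF, leaves the difference almost unchanged (0.52 → 0.51).

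**Which baseline.** SAP 4.4.3.1 refers to each cycle's own baseline, but SAP 4.1 defines the baseline for cycles after the first as the "last available valid measurement within 3 days before the start of study medication on Cycle 1 Day 1". SAP Appendix 4 windows the later Day 1 sample relative to Day 1 of each cycle. How often T ≥ B in a later cycle depends on which anchor applies.

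**The case against.** The strongest reply is that the parenthesis only describes what a trough usually is, in translated text. No sentence says that a cycle without a fall is dropped. Where the SAP means to exclude, as in Strategy 2 for patients without severe neutropenia, it says so. This stands in part: exclusion is a consequence of the wording and the no-imputation rule, not an instruction. If the clause is only descriptive, though, it does no work, and removing it avoids two programmers deriving different data.

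Three stronger readings are tempting, and the documents do not support them.

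- A reader might infer that well-protected patients leave the endpoint altogether. The summary is by cycle, so a patient without a trough in Cycle 3 can still contribute in Cycle 1. A cycle without a fall may also reflect G-CSF or a low cycle baseline rather than protection.
- A reader might infer that the bias always runs against trilaciclib, by some fixed percentage. The last table row shows it can reverse. That row applies any-cycle G-CSF rates to every cycle, which probably overstates use, and at half those rates the difference is again understated. The direction is therefore unsettled.
- A reader might infer that the efficacy conclusion is at risk. The endpoint is descriptive. SAP 4.4.3.2 summarises ANC at every visit, with no below-baseline condition. DSN and severe neutropenia incidence keep patients without an event.

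The split by G-CSF in SAP 4.4.3.1 is no remedy: the restriction operates within each subset, and G-CSF use is itself post-randomisation.

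**Conclusion.** The point holds as a defect in the definition. As written, the clause leaves some patient-cycles without a trough, forces every baseline-to-trough change to be negative, and conditions the comparison on an outcome affected by treatment and by G-CSF. Loss is likelier after Cycle 1.

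If G-CSF plays no part, the trilaciclib effect on the trough is understated, by about 8% to 55% under the assumed Day 8 and next Day 1 ratios. With heavier G-CSF use on placebo the bias can go the other way. Nothing in the documents settles the size. The matter is minor: one descriptive other secondary endpoint is affected, and the primary and key secondary analyses are not.

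**What to change.** Delete the parenthesis in SAP 4.4.3.1. Suggested replacement: the cycle trough is the lowest post-dose ANC between the start and end of the cycle, whether or not it is below the cycle baseline; it is summarised for all patients with at least one post-dose ANC in that cycle; the number of cycles without one is reported by arm.

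In the same edit, reconcile the later-cycle baseline in SAP 4.1 with the cycle-specific baseline that SAP 4.4.3.1 uses, since the change from baseline depends on it.

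The cost is two short text edits and the matching derivation. No new data, visits or sample size are needed.

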4.4.3.3. Other dichotomous endpoints

The total number of events below is the total number of cycles with at least one event. If a patient does not experience any of the following events during the treatment period, the number of events for that patient is zero. 'Yes' if ≥ 1 of the following events are observed; otherwise 'No'.

- Incidence of Grade 3 and 4 Hematologic Toxicities: Grade 3 and 4 hematologic toxicities refers to hematology laboratory results with CTCAE Grade 3 or 4.
- Incidence of platelet transfusion (during chemotherapy)
- Incidence of febrile neutropenia

Each of the following events with a unique start date will be defined as a separate event during the treatment period. Yes if the total number of the following events observed is ≥ 1 , otherwise no.

- Incidence of intravenous or oral antibiotics
- Incidence of infectious serious adverse events
- Incidence of serious adverse events of lung infection

Determine if the following medications is used in that cycle by comparing the start and end dates of each use of the following medications with the start and end dates of the treatment cycle. The total number of events with the following medications is the total number of cycles with at least one dose of the following medication. If a patient did not take the following medications during the treatment period, the number of events for that patient is 0.

- Erythropoiesis-stimulating agent (ESA) Usage
- Recombinant human interleukin-11 (IL-11) use rate
- Thrombopoietin (TPO) use

The total number of events as well as the incidence of the above dichotomous variables will be summarized descriptively and tabulated in detail by patient. The statistical analysis approach is similar to that described for SN incidence in Section 4.4.2.1, except that baseline ANC measurements will not be included as covariates in the modified Poisson regression model.

In addition, for comparing the incidence of antibiotic administration, SAEs of infection, and SAEs of lung infection between the Trialciclib and placebo groups, the offset variable in the modified Poisson regression model will be the log transformed duration of treatment (weeks) rather than the number of cycles.

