4.1. Criteria for enrollment

Criteria for enrollment

Patients must meet all of the following inclusion criteria to be enrolled in the study:

- 1. Age \geq 18 years, male or female;
- 2. Histologically or cytologically confirmed extensive stage small cell lung cancer (ES-SCLC):
- Patients scheduled to receive carboplatin plus etoposide regimen: no prior systemic therapy (eg, chemotherapy or combined with immunotherapy);
- Patients scheduled to receive topotecan regimen: previously received 1/2 lines of chemotherapy or combined immunotherapy but not topotecan.

3. Presence of at least one radiation-naïve measurable lesion according to RECIST 1.1 criteria;

- 4. Hemoglobin \geq 90 g/L;
- 5. Neutrophil count $\geq 1.5 \times 10^9$ /L;
- 6. Platelet count $\geq 100 \times 10^9$ /L;
- 7. Creatinine $\leq 15 \text{ mg/L}$ or creatinine clearance (CrCl) $\geq 60 \text{ mL/min}$ (Cockcroft-Gault formula);
- 8. Total bilirubin $\leq 1.5 \times$ upper limit of normal (ULN);
- 9. Alanine aminotransferase (ALT) and aspartate aminotransferase (AST) \leq 3 × ULN or
- \leq 5 × ULN (for patients with liver metastases);
- 10. Albumin \geq 30 g/L;
- 11. ECOG PS score 0 2;
- 12. Expected survival time \geq 3 months;
- 13. Contraception:

Females: All females of childbearing potential must have a negative serum pregnancy test at screening and must use reliable contraception from signing of informed consent through 3 months after the last dose;

Male: Female partners of childbearing potential must use reliable contraception from signing the informed consent until 3 months after the last dose;

14. Understand and sign informed consent.

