7.2. Safety evaluation

7.2.1. Clinical laboratory tests

Blood samples for hematology, urinalysis, and blood chemistry will be collected according to the trial flow chart and analytical testing will be completed at a local laboratory.

- Blood routine: white blood cell (WBC), red blood cell (RBC), hemoglobin (Hb), platelet (PLT), hematocrit (HCT), neutrophil (NEU), eosinophil (EOS), basophil (BAS), monocyte (MON), lymphocyte (LYM), etc.;
- Urinalysis: urine protein, urine pH, urine ketone body, urine glucose, urine red blood cells, urine white blood cells, etc. Note: 24-hour urine protein quantification is required for subjects with urine protein ≥ ++;
- Blood biochemistry: aspartate aminotransferase (AST), alanine aminotransferase (ALT), γ-glutamyltransferase (γ-GT), lactate dehydrogenase (LDH), cholesterol (TC), triglyceride (TG), total bilirubin (TBIL), direct bilirubin (DBIL), total protein (TP), albumin (ALB), alkaline phosphatase (ALP), creatine kinase (CK), glucose (GLU), uric acid (UA), blood urea nitrogen (BUN)/urea (Urea), creatinine (Cr), sodium (Na), potassium (K), calcium (Ca), phosphorus (P), magnesium (Mg) and chloride (Cl);
- Serum pregnancy test (females of childbearing potential only), For female subjects of childbearing potential, serum pregnancy test will be performed before the start of administration. After negative results of pregnancy test in the screening period, reliable contraceptive measures should be started;

Note: Females who were not of childbearing potential were permanently sterilized

(hysterectomy, bilateral oophorectomy, or bilateral salpingectomy) and postmenopausal. A woman ≥ 50 years of age was considered postmenopausal if she had been amenorrheic for 12 months prior to the planned date of randomization and had no other medical etiology. A woman < 50 years of age is considered postmenopausal if she has been amenorrheic for 12 months or more after stopping exogenous hormone therapy and has follicle-stimulating hormone (FSH) levels in the postmenopausal range.

• Virology:

Hepatitis B and C screening were performed during the screening period, five items of hepatitis B: if hepatitis B surface antigen (HBsAg) was positive or hepatitis B core antibody (HBcAb) was positive, HBV-DNA should be added; hepatitis C examination: if hepatitis C antibody was positive, HCV-RNA should be added.

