4.6.2. Adverse Events

Adverse events will be monitored from the time of informed consent through the end of the safety follow-up period, initiation of new antineoplastic therapy, or withdrawal from the study, whichever comes first. Adverse events will be graded and recorded according to NCI-CTCAE version 5.0 throughout the study and during follow-up.

Only treatment-emergent adverse events (TEAEs) will be summarized. A TEAE is defined as any untoward medical occurrence or an adverse event that worsened relative to pretreatment state that emerged newly from the first dose of study drug through 30 days after the last dose or before the start of new anticancer therapy. AE will be coded according to the International Conference on Harmonisation (ICH) Medical Dictionary for Regulatory Activities (MedDRA) and the number and incidence will be summarized by System Organ Class (SOC) and Preferred Term (PT). Serious adverse events after medication, adverse events leading to dose reduction, delay or discontinuation, adverse events leading to dropout, adverse events leading to death, adverse events of special interest, drug-related adverse events, etc. will be summarized separately, and the details of each adverse event for each patient will listed, including the type, severity, occurrence and duration, outcome of adverse events, and the relationship with the study drug.

For summarizing TEAE, the incidence of adverse events will be calculated based on the number of patients with adverse events rather than the number of adverse events. When calculating the number and percentage of patients with adverse events, one patient with multiple occurrences of the same adverse event will only be counted one.

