4.6.3. Clinical Laboratory Tests

Hematology and blood chemistry test results at baseline and each visit time point and corresponding changes from baseline will be summarized descriptively and listing will be provided in detail. CTCAE grades for hematology and blood chemistry will be determined according to the laboratory parameter CTCAE criteria(see Appendix 3). CTCAE Version 5.0 will be used for grading. According to CTCAE Version 5.0, CTCAE grading of some items requires clinical diagnosis or joint judgment of clinical diagnosis and values, which cannot be completely divided by programming, such as hyperglycemia, hypokalemia, hypophosphatemia, hyponatremia and hyperuricemia, CTCAE Version 4.03 will be used for grading. Patients' changes from baseline CTCAE grade to worst postdose CTCAE grade will be summarized using cross-classification tables. Grade 3 or 4 hematology and blood chemistry laboratory abnormalities occurring during treatment will also be summarized separately, as appropriate. Urinalysis results will be presented in listings only.

Actual study days for patients may differ from planned study days between the first dose of study drug in each cycle and the scheduled visit date. In this case, visit-based summaries will categorize assessments based on visit within time window as shown in Appendix 4.

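### The Grade 3/4 haematologic toxicity endpoint requires no worsening from baseline, so Grade 3 lymphopenia present at entry and not due to prior therapy would count as toxicity

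*SAP*

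**What the plan says.** SAP 4.4.3.3 defines the endpoint by laboratory grade alone: "Grade 3 and 4 hematologic toxicities refers to hematology laboratory results with CTCAE Grade 3 or 4". The counting rule is "The total number of events below is the total number of cycles with at least one event", and a patient is a yes if at least one event is seen in the treatment period. Neither rule refers to the baseline grade or says that the result must be post-baseline.

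The analysis follows the severe neutropenia incidence analysis in SAP 4.4.2.1: modified Poisson regression with a log-cycles offset and a two-sided p-value, plus a stratified exact CMH test. It applies here "except that baseline ANC measurements will not be included as covariates in the modified Poisson regression model". No other baseline count takes its place.

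The haematology panel is broad. SAP Appendix 2, footnote g, ends its list with "basophil (BAS), monocyte (MON), lymphocyte (LYM), etc", and Protocol 7.2.1 gives the same components. SAP Appendix 3 grades lymphocytes and leucocytes alongside haemoglobin, neutrophils and platelets.

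Elsewhere the SAP does look back to baseline. Section 4.6.2 says "A TEAE is defined as any untoward medical occurrence or an adverse event that worsened relative to pretreatment state". For safety laboratory data, section 4.6.3 says "Patients' changes from baseline CTCAE grade to worst postdose CTCAE grade will be summarized using cross-classification tables". Section 4.4.3.1 restricts neutrophil troughs to values below the cycle baseline.

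**The concern.** The endpoint is named as a toxicity, but the rule counts a state. A patient who enters with a Grade 3 lymphocyte count and stays there is scored as having chemotherapy toxicity, although neither chemotherapy nor trilaciclib caused it. Such events fall in both arms and, on average, pull the comparison toward no difference. In arms of about 40 a few such patients can also be unevenly split by chance. The model has no baseline count that could absorb this, and the safety shift tables do not alter the efficacy estimate or its p-value.

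**Working it through.** The plan states no rate, power or sample size for this endpoint, so there is no figure to reproduce. The check has two parts: who can enter at Grade 3/4, and how much this could matter.

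**1. Entry limits against Grade 3 thresholds.** Floors are from Protocol 4.1 and grades from SAP Appendix 3. Counts are x10^9/L and haemoglobin is g/L.

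| Parameter | Entry floor | Grade 3 starts below | Grade 3/4 possible at entry? |
|---|---|---|---|
| Haemoglobin | 90 | 80 | No |
| Neutrophils | 1.5 | 1.0 | No |
| Platelets | 100 | 50 | No |
| Lymphocytes | none | 0.5 | Yes, if not due to prior therapy |
| Leucocytes | none stated | 2.0 | Only from 1.5 to 2.0 |

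Leucocytes include neutrophils, so the neutrophil floor implies leucocytes of at least 1.5. Grade 4 leucopenia (below 1.0) is therefore impossible at entry. On a sample with leucocytes below 2.0 and neutrophils of at least 1.5, lymphocytes are below 2.0 - 1.5 = 0.5, which is already Grade 3. The leucocyte route therefore adds a second affected parameter but no further patients.

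**2. Who remains after exclusion 12.** Protocol 4.2 excludes patients whose toxicity from prior anticancer therapy has not recovered to Grade 0 or 1, with only alopecia exempt. That covers treatment-related lymphopenia in second- and third-line patients. First-line patients have had no systemic therapy, so this criterion does not reach disease-related or intrinsic lymphopenia in them.

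**3. Would it be recorded again?** From Cycle 2, haematology is drawn on Days 1 and 8 (EC) or Days 1 and 10 (topotecan). The Day 1 conditions in Protocol 5.4.2 name neutrophils, platelets and non-haematologic toxicity, not lymphocytes. A persistent low count could therefore recur without delaying the next cycle, giving up to 6 events over 6 EC cycles.

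**4. Yes/no variable.** Let p be the share of each arm with persistent Grade 3/4 lymphopenia from entry, assumed equal in both arms and unrelated to the risk of a new event. With incident rate r:

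observed rate = p + (1 - p) x r

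difference = (1 - p) x (r placebo - r trilaciclib)

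Protocol 1.3.1 gives Grade 3 or 4 haematologic TEAE rates of 77.1% (placebo) and 44.3% (trilaciclib). They stand in for laboratory rates, which the documents do not give in pooled form. Power is approximate, for two proportions at 40 per arm.

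| p (assumed) | Trilaciclib | Placebo | Difference (points) | Ratio | Power |
|---|---|---|---|---|---|
| 0% | 44.3% | 77.1% | 32.8 | 0.575 | 87% |
| 2% | 45.4% | 77.6% | 32.1 | 0.586 | 85% |
| 5% | 47.1% | 78.2% | 31.2 | 0.602 | 84% |
| 10% | 49.9% | 79.4% | 29.5 | 0.628 | 80% |

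At 5% the loss is 0.05 x 32.8 = 1.6 points; at 10% it is 0.10 x 32.8 = 3.3 points.

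**5. Cycle count.** Assume per-cycle rates of 0.50 (placebo) and 0.25 (trilaciclib), a true ratio of 0.50, and that affected patients score in every cycle.

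- p = 5%: (0.05 + 0.95 x 0.25) / (0.05 + 0.95 x 0.50) = 0.2875 / 0.525 = 0.55
- p = 10%: (0.10 + 0.90 x 0.25) / (0.10 + 0.90 x 0.50) = 0.325 / 0.55 = 0.59

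**6. Chance imbalance.** With independent binomial counts in two arms of 40, the arms differ by 2 or more such patients with probability about 21% at p = 2% and 43% at p = 5%.

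**The case against.** The strongest objection is that the affected group may be very small or empty. Three of the five graded parameters are protected at entry, exclusion 12 closes the treatment-related route, and nothing in the documents shows that spontaneous Grade 3 lymphopenia occurs in this population. This stands: p = 0 belongs in the range.

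Second, SAP 4.4.3.3 does not say that parameters are pooled. Protocol Table 3 reports haemoglobin and platelets in separate rows, and the synopsis names only Grade 3/4 anaemia in its list of other secondary endpoints. By-parameter reporting would confine the problem to the lymphocyte row and, marginally, the leucocyte row. This also stands, but it would not remove the problem from those rows.

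Third, six events in six cycles is no special leverage. The log-cycles offset makes it a rate of one per cycle, as for any patient with a Grade 3/4 nadir each time. That is right.

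Fourth, shift tables and summaries of lymphocytes by visit are planned, so a reader could see pre-existing lymphopenia. True, but they do not correct the efficacy comparison.

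A reader might infer that eligibility leaves lymphopenia unrestricted and that an affected patient scores in every cycle. The documents do not support that. Exclusion 12 is a real limit, a Grade 1 or 2 baseline does not score by itself, and a cycle counts only if a Grade 3/4 result is recorded in it.

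**Conclusion.** The point holds in a narrow form. The definition is explicit and has no baseline condition. Grade 3 lymphopenia not attributed to prior therapy, with or without leucocytes of 1.5 to 2.0 x10^9/L, can be present at entry and would be counted as toxicity wherever it is recorded.

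The expected effect is a small dilution toward no difference: 0 to about 3.3 of 32.8 points on the yes/no variable for an assumed prevalence of 0-10%. The prevalence, its equality between arms, the use of TEAE rates for laboratory rates, and pooling across parameters are all assumptions. If only first-line patients are affected, the prevalence across the whole arm is lower than it is within that stratum.

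It would be wrong to read this as a bias in favour of trilaciclib or as a threat to the trial's main conclusion. On average the dilution works against finding a difference, though a chance imbalance could go either way. No stated sample size, power or alpha rests on this endpoint, and DSN and the key secondary endpoints are unaffected. It is a low-priority improvement.

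**What to change.** In SAP 4.4.3.3, define the event as a post-baseline haematology result of CTCAE Grade 3 or 4 that is a higher grade than the study baseline for the same parameter. Apply this to both the yes/no variable and the count of cycles. Name the parameters that count, and report each one separately. A new Grade 4 neutropenia in a patient with baseline lymphopenia would still score, because the comparison is made within each parameter.

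The cost is a short change to the SAP text and minor programming, since baseline grades are already needed for the shift tables in SAP 4.6.3. There is a small downside. A patient at Grade 3 at baseline can score only at Grade 4, and a patient at Grade 4 at baseline cannot score for that parameter, yet both remain in the denominator. State the number of such patients, by arm and parameter, beside the result.
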